Baseline and Follow up Assessments (6-week, 3, 6, 9-month) measures (45 minutes [baseline, 6 week, 3 month] or 25-30 minutes [6 month, 9 month]). While the baseline and follow-up measures contain overlapping content, we may decide to include or exclude a measure over the course of the study, with IRB approval via a modification. Thus, we are electing to not indicate in the consent form that the surveys will all be the same. Overlap in surveys is indicated by the overall content areas of surveys that are provided in the consents. Behavior will be reported over lifetime (baseline), past 6 weeks (6-week assessment), and 3 months (3, 6, 9-month follow ups) to reduce problems with retrospective recall and overlap. Demographics will include age, height, weight, family history characteristics. Items assessing the types of events students would be interested in hearing about will be included in the Baseline survey only. We have added items to the follow-up surveys about past and current events they attend or like. There are also items in the Demographics measure in the Baseline survey only relevant to the personalization of the 6-week text message intervention. Social phobia will be measured at 6-week and 3-month only using the Social Interaction Anxiety Scale ($\alpha = .94$; Mattick & Clarke, 1998; Lindner et al., 2013). Family history of alcohol, age of first use, and lifetime alcohol use will be assessed in the baseline survey and all follow-up timepoints (Johnston et al., 2014; Miller & Marlatt, 1984). Perceived vulnerability will be assessed by asking participants how likely they think it is that certain alcohol consequences will happen to them ($\alpha = .82$; Gerrard et al., 2008; Johnston et al., 2011). We will assess the frequency participants view/share posts on a variety of social networking sites related to alcohol and marijuana use using the Social Media Scale. To determine drinking initiation, questions will ask when the behavior was initiated. Drinking will be assessed with the Daily Drinking Questionnaire and Quantity Frequency Index (DDQ; $\alpha = .73$; Collins et al., 1985; Dimeff et al., 1999; [name] & Neighbors, 2004). College drinking influences will be measured using the College Drinking Influences Survey at 6-week and 3-month only ($\alpha = .71-.94$; Fisher et al., 2007). Consequences will be assessed with the Young Adult Alcohol Consequences Questionnaire ($\alpha = .79$; Read et al., 2006, 2007). Reasons for not drinking will be assessed using the Reasons for Not Drinking Scale ($\alpha = .79$; Huang, 2011). The willingness measure will assess willingness to use alcohol in certain scenarios ($\alpha = .85$; Gerrard et al., 2002, 2008). Intentions for alcohol use will be assessed by items on intended frequency and quantity ($\alpha = .83$; Ajzen, 2006; Gerrard et al., 2006). Injunctive norms will be measured using statements that assess participants' perceptions of other's attitudes towards abstaining or drinking lightly ([name] et al., 2010; Krieger et al., 2016). Descriptive norms will be measured by items that assess the perceived frequency and quantity of others' drinking using the Drinking Norms Rating Form (Baer et al., 1991). Prototypes will be measured by items that assess how favorable and similar participants feel toward the typical abstainer and lighter drinker of the same sex and age ($\alpha = .87$; Gerrard et al., 2002). We will assess urgency, sensation seeking, premeditation, and perseverance using the UPPS Impulsive Behavior Scale ($\alpha = .82-.91$; Whiteside & Lynam, 2001, 2003). Alternative activities will be assessed by asking how favorable participants feel toward alcohol-free activities as well as an open-ended item that asks participants what sorts of activities they enjoy doing that do not involve alcohol use. The Fear of Missing Out scale (FoMO; $\alpha = .90$; Przybylski

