To explore treatment differences and to determine preliminary effect sizes in drinking outcomes, this pilot will have five repeated measures (i.e., baseline, 6-week post-intervention, 3, 6, and 9-month follow-ups), yielding up to 1500 Level 1 observations (repeated-measures) across 300 Level 2 cases (people). Prior to inferential statistics, univariate and bivariate descriptive statistics will be used to assess distributions and simple associations among variables. Primary outcomes are alcohol initiation (binary outcome) and escalation in terms of number of drinks and consequences (both count outcomes). Additional outcomes are abstainer prototype favorability, abstainer injunctive and descriptive norms, engagement in and enjoyment of alternative activities, and endorsement of personal goals that do not involve alcohol, which are modeled as normally distributed outcomes. Given the repeated measures design, generalized linear mixed models (GLMM; Raudenbush & Bryk, 2002) will be used. GLMM (aka hierarchical generalized linear models) allow for non-normal outcomes and missing data. The model below represents the basic analytic model for a count outcome:

$$\text{Level 1: } \log(E[DV_{ti}]) = \pi_{0i} + \pi_{1i}(6\text{-week})_{ti} + \pi_{2i}(3\text{-month})_{ti} + \pi_{3i}(6\text{-month})_{ti} + \pi_{4i}(9\text{-month})_{ti} \quad (1)$$

$$\begin{aligned} \text{Level 2: } \pi_{0i} &= \beta_{00} + \beta_{01}(Tx)_i + r_{00i} & \pi_{3i} &= \beta_{30} + \beta_{31}(Tx)_i + r_{30i} \\ \pi_{1i} &= \beta_{10} + \beta_{11}(Tx)_i + r_{10i} & \pi_{4i} &= \beta_{40} + \beta_{41}(Tx)_i + r_{40i} \\ \pi_{2i} &= \beta_{20} + \beta_{21}(Tx)_i + r_{20i} \end{aligned}$$

where t indexes time point and i indexes participants. DV_{ti} represents the outcome for each individual at each time point. Time will be coded with *four* dummy variables (6-week $_{ti}$, 3-month $_{ti}$, 6-month $_{ti}$, and 9-month $_{ti}$) that compare follow-up assessments to baseline (reference category). Tx is a dummy coded variable comparing the TM intervention condition to the AOC condition. We will test sex and age in all analyses. We will determine preliminary effect sizes using the

model shown in equation 1. The four treatment by time interactions (β_{11} to β_{41}) compare the change in the outcome since baseline between intervention and control.

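### The planned change-since-baseline mixed model cannot give a usable effect size for alcohol initiation, the binary primary outcome

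*Protocol*

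**What the plan says.** Protocol, Data Analysis and Power, sets out the outcomes: "Primary outcomes are alcohol initiation (binary outcome) and escalation in terms of number of drinks and consequences (both count outcomes"). The additional outcomes (prototypes, norms, alternative activities, personal goals) are ones "which are modeled as normally distributed outcomes". Generalised linear mixed models are named as the method because of the repeated measures, "yielding up to 1500 Level 1 observations (repeated-measures) across 300 Level 2 cases (people").

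One equation follows, introduced thus: "The model below represents the basic analytic model for a count outcome". It has a log link, four time dummies with baseline as reference, a treatment term in every Level 2 row and a person-level residual in every Level 2 row. No covariance is stated for the five residuals. The text then says "We will determine preliminary effect sizes using the" model in equation 1, and reads the four treatment-by-time terms as differences in change since baseline. No link, at-risk group, baseline coding or random-effects structure is written for initiation.

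In the measures section (Baseline and Follow up Assessments), "To determine drinking initiation, questions will ask when the behavior was initiated", and "age of first use, and lifetime alcohol use will be assessed in the baseline survey and all follow-up timepoints". The same section has behaviour reported over the lifetime at baseline, over 6 weeks at the 6-week survey and over 3 months after that. Section F.2 admits students who drink up to once a week on average. The SAP's Analytic Plan reports initiation rates at each time point and names no model.

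**The concern.** Aim 3 wants preliminary effect sizes to plan a later R01. For initiation, the stated route is a mixed model with an interaction against baseline. The measures section points towards first use, although no full definition is given. First use is a one-way event: once a student has drunk, the answer stays yes. A mixed logit gives positive probability to every reversal, so it is at odds with such data. A change-from-baseline contrast also needs a baseline that can vary. Among never-drinkers it is zero by definition, and students who already drink are fixed at one throughout. If initiation instead means current drinking, the outcome can reverse, but lifetime reporting at baseline is being compared with 6-week or 3-month reporting later.

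At stake is the model-based effect size for one of the three primary outcomes. A person-specific log-odds ratio taken from such a fit into an R01 power calculation could be wrong by a large factor.

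**Working it through.** **Inputs.** From the protocol: 300 people, 5 assessments, 150 per arm. Check: 300 x 5 = 1500 observations, as stated. The documents give no initiation rates, correlations or share of never-drinkers, so those below are assumptions. Follow-up is taken as complete.

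**1. First use, all participants, random-intercept logit.** Assumed cumulative rates at the five assessments: control 40/45/50/55/60%, intervention 40/41/44/48/52%. With no reversals, only six response patterns can occur per arm.

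- Saturated deviance = -2 x 150 x sum of p ln p in each arm. Control (patterns 40, 5, 5, 5, 5, 40%): 399.65. Intervention (40, 1, 3, 4, 4, 48%): 338.27. Total 737.9.
- Ten free fixed effects, maximised at a fixed intercept SD:

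| Intercept SD | Deviance | 9-month interaction (log-odds) |
|---|---|---|
| 2 | 1145.7 | -0.68 |
| 8 | 809.3 | -1.82 |
| 32 | 743.1 | -5.87 |
| 128 | 738.0 | -25.7 |

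The fit keeps improving towards the saturated value and never reaches it. With finite parameters some probability always goes to reversals; that probability vanishes only as the SD goes to infinity. So no finite maximum exists. The five-residual structure contains the random intercept as a special case, so it does not help. The marginal 9-month odds ratio in the same data is (0.52/0.48)/(0.60/0.40) = 0.72 in every row. A lower-rate set (20/26/31/36/41% against 20/22/25/29/33%) behaves alike: deviance 1010.8, 736.2 and 686.9 at SD 2, 8 and 32 (saturated 684.8), with interactions -0.68, -1.78 and -6.23.

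**2. Inconsistent answers.** Flip each answer in the first set with probability 0.001, 0.005, 0.01 or 0.02, which gives about 1, 6, 11 or 22 of 300 people a reversal. The estimate is then finite, but the interaction is -5.0, -2.7, -1.9 or -1.4. The data's marginal odds ratio stays at 0.72 to 0.73.

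**3. First use among never-drinkers, baseline row kept.** Every baseline value is 0, so the baseline log-odds is minus infinity. In an illustrative logistic fit of equation 1's fixed part, the intercept ran to -11.6, -26.6 and -39.3 at 10, 25 and 50 iterations, and the SE of the 6-week interaction rose from 23 to 7.8 million. Without the baseline rows the 6-week contrast was -0.18 (SE 0.34).

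**4. What a marginal contrast delivers.** Never-drinkers assumed to be 30, 50 or 70% of 300 (45, 75 or 105 per arm), with 9-month rates of 35% against 25%. Risk-difference SE = sqrt[(0.35 x 0.65 + 0.25 x 0.75)/n] = 0.096, 0.074 or 0.063. Log odds ratio SE = sqrt[(1/0.2275 + 1/0.1875)/n] = 0.47, 0.36 or 0.30.

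**5. Normal outcomes.** With equal variances, equation 1 estimates a difference in change: SE = sqrt[2(1 - rho) x 2/150] SD. Setting the baseline treatment term (beta01) to zero, or adjusting for baseline, gives sqrt[(1 - rho^2) x 2/150]. The variance ratio is 2/(1 + rho).

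| Assumed rho | Change SE | Adjusted SE | Variance ratio |
|---|---|---|---|
| 0.3 | 0.137 | 0.110 | 1.54 |
| 0.5 | 0.115 | 0.100 | 1.33 |
| 0.7 | 0.089 | 0.082 | 1.18 |

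**The case against.** **The equation is only for counts.** True: it is labelled so, and the protocol does name the model class and each outcome's distribution. A reader might infer that no model is given at all; the text does not support that. What is missing is the specification for initiation. The paragraph's stated purpose is effect sizes in drinking outcomes, which includes initiation.

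**Five residuals for five observations.** A reader might infer that equation 1 is unidentified for every outcome. It is not. For a Poisson count, 15 covariance parameters meet 15 moments. For normal outcomes a free covariance plus residual variance gives 16 parameters against 15 moments, but only the variance split is lost; a diagonal covariance (6 parameters, rank 6) is identified. Since the covariance is unstated, failure cannot be read into it. The first-use result does not rely on this, because it already occurs with a single random intercept.

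**The large interactions are a matter of scale.** Partly fair. The SDs in step 1 are imposed. In the misreporting fits, averaging the model back to the marginal scale gives a 9-month odds ratio of 0.75 to 0.77 against 0.72 to 0.73 in the data, a modest bias. But the protocol takes its effect sizes from the interaction terms and plans no such averaging.

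**This is a pilot and the SAP is descriptive.** Also fair, and it limits the damage. It does not settle whether the protocol's model-based effect sizes are still intended.

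**Conclusion.** The point holds for alcohol initiation. Under the first-use reading, which the measures section favours, the planned interaction has no finite estimate with complete, consistent data. With a few inconsistent answers it is set largely by how many there are: -5.0 to -1.4 for about 1 to 22 people in 300, on data whose marginal odds ratio hardly moves. Under the current-drinking reading, change from baseline compares different recall windows. These sizes rest on assumed rates and full follow-up; the absence of a finite estimate rests only on irreversibility and consistent answers.

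The scope is narrow. It would be tempting to extend the point to the baseline row for normal outcomes, but that row simply estimates an ordinary mean, and the treatment effects there are valid. The cost is precision: variance 1.18 to 1.54 times as large for rho from 0.7 to 0.3. The count model is not in question on this point, and neither are the descriptive rates in the protocol and SAP. This should be fixed, but it does not threaten the feasibility and acceptability aims.

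**What to change.** **Protocol, Data Analysis and Power.**
1. Define initiation as first use by each follow-up among participants with no lifetime use at baseline. Drop the baseline row. Report a risk difference or marginal odds ratio at each time point, by logistic regression or by GEE with robust SEs. If current drinking is meant, use the same marginal contrast at follow-up, not change from the lifetime baseline.
2. For normal outcomes measured at baseline and follow-up, set beta01 to zero or adjust for the baseline value. Personal goals are listed as an outcome here, but the measures section appraises them at baseline only; exclude them or reconcile the two sections.
3. Leave the count model as it is on this point.

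**SAP, Analytic Plan.** Cite these analyses, or state that effect sizes will not be model-based.

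**Cost.** A few sentences and no new data, since first use and lifetime use are already collected. There are three downsides. The initiation analysis uses fewer people. Its effect is marginal, not person-specific, so the R01 calculation must use that scale. GEE or separate logistic regressions need a somewhat stronger missing-data assumption than a likelihood model, which reported dates of first use partly offset.

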Online screening survey: 5-10 minutes

Online baseline survey: 45 minutes

6 weeks Intervention Content: 1-2 minutes per text message

Online 6-week, 3-month surveys: 45 minutes

Online 6-month, 9-month surveys: 25-30 minutes

Online interview: 60 minutes

F. Human Subjects - Describe the characteristics of the research population:

- 1) *Sample Size*: Number of subjects to be enrolled in this study at this site. Approximately 300 subjects at 1 sites in the U.S. will be enrolled in the study overall. Half of the subjects (150) will be randomized to the TM intervention and the other half to the control group.
For Clinical Trial studies, indicate number of subjects to be randomized N/A
- 2) Describe both *Inclusion AND Exclusion Criteria*. BE SPECIFIC! Also, if children (persons under age 18) are excluded from this study provide scientific justification for such exclusion. Include physical, mental, cognitive, medical, and other relevant Inclusion and Exclusion criteria.

Inclusion criteria:

- 1) Age 18-19 (If a participant screens in at age 19 and turns 20 prior to the start of the pilot study, the participant will be allowed to be in the research study.)
- 2) Birthdate that is consistent with their given age

- 3) First-year college student at the University of North Texas
- 4) Valid email address
- 5) Provide a valid mobile phone number and have a text messaging plan on their mobile phone
- 6) Consumed alcohol on average once a week or less in the last month
- 7) No episodes in the past month of consuming 5/4 drinks in the past month for men/women
- 8) Used marijuana once a week or less on average in the last month
- 9) Express any level of willingness to take a sip of alcohol
- 10) If female, must not be pregnant or trying to get pregnant
- 11) Have not received treatment for alcohol use
- 12) Willing to participate in the pilot study

Exclusion criteria include not meeting inclusion criteria, unwillingness to participate, failure to provide consent (e.g., declining participation in the study), providing inconsistent responses (e.g., age) identified by the survey, and having already participated in the study (IRB 2018-128 or this protocol) as identified by overlap or consistency in computer IP addresses, contact information, and demographics.

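### Alcohol initiation is a binary primary outcome with no event rule, at-risk set or denominator although current drinkers are eligible, and whether the baseline-referenced interactions can estimate it depends on the coding

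*Protocol*

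**What the plan says.** **Outcome.** Protocol, Data Analysis and Power: "Primary outcomes are alcohol initiation (binary outcome) and escalation in terms of number of drinks and consequences (both count outcomes". The SAP's Analytic Plan says only that yes/no initiation rates were looked at by time point.

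**Measurement.** Protocol, Baseline and Follow up Assessments: "To determine drinking initiation, questions will ask when the behavior was initiated". Also: "Family history of alcohol, age of first use, and lifetime alcohol use will be assessed in the baseline survey and all follow-up timepoints". The same paragraph sets recall windows for behaviour: lifetime at baseline, 6 weeks at the 6-week survey, and 3 months at the later surveys.

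**Who is enrolled.** Protocol section F.2, criterion 6: "Consumed alcohol on average once a week or less in the last month". This admits never-drinkers, past drinkers and current light drinkers. Criterion 9 reads: "Express any level of willingness to take a sip of alcohol".

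**Model.** The drinking-outcome analysis is described as "yielding up to 1500 Level 1 observations (repeated-measures) across 300 Level 2 cases (people"). Time enters as four dummy variables "that compare follow-up assessments to baseline (reference category"). Effect sizes come from equation 1, whose four treatment-by-time interactions "compare the change in the outcome since baseline between intervention and control". Equation 1 is presented as the version for a count. No binary version is written out, and initiation is not exempted.

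**The concern.** Delaying initiation is in the trial's title, and the Data Analysis section says these rates will supply base rates for powering a future R01. A binary outcome can serve that purpose only if a reader can tell who is able to have the event and what a 1 means at each wave. The named survey items suggest first-ever use. On that meaning, a student who already drinks at baseline cannot initiate. The plan nevertheless counts all 300 people at all five waves and measures the effect as a difference in change from baseline. It does not say whether baseline drinkers are excluded, coded 1 throughout, or coded 0 throughout. Each choice gives a different control rate and effect size from the same answers, and one family of choices leaves the named effect size without a finite estimate.

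**Working it through.** **1. The plan's own figure.** 300 people × 5 assessments = 1500 observations, and 300 / 2 = 150 per arm. Both reproduce. The 1500 includes the baseline row and anyone who had already started drinking. The documents give no initiation rate, never-drinker share, alpha or target effect, so there is nothing further to reproduce.

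**2. Everyone analysed is 0 at baseline** (new-onset scoring, or never-drinkers with the baseline row kept). The likelihood keeps rising as the baseline log-odds in both arms go to minus infinity, so the change since baseline is unbounded in each arm and β11 to β41 have no finite estimate. A plain logistic fit shows this (75 never-drinkers per arm; 37 control and 26 intervention events at follow-up):

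| Iterations | Baseline intercept | SE of interaction |
|---|---|---|
| 10 | −11.6 | 32 |
| 20 | −21.6 | 4,774 |
| 30 | −31.6 | 708,471 |

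The printed interaction stays near −0.61 only because the two arms' baseline terms diverge in step; the growing SE shows that it is not identified. Comparing the arms at follow-up only, on the same data, gives an odds ratio of 0.545 with a log-odds-ratio SE of 0.335.

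**3. Baseline drinkers kept in the denominator.** Let s be the never-drinker share, and let first use by 9 months among never-drinkers be 50% (control) and 35% (intervention). All three inputs are assumptions.
- Drinkers coded 1 (ever-use): control = (1 − s) + 0.50s; intervention = (1 − s) + 0.35s.
- Drinkers coded 0: control = 0.50s; intervention = 0.35s.
- The risk difference is 0.15s under both codings, against 0.15 in never-drinkers.

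At s = 0.5:

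| Scoring | Control | Intervention | Risk difference | Odds ratio |
|---|---|---|---|---|
| Never-drinkers only | 50% | 35% | 15 points | 0.54 |
| All, drinkers coded 1 | 75% | 67.5% | 7.5 points | 0.69 |
| All, drinkers coded 0 | 25% | 17.5% | 7.5 points | 0.64 |

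At s = 0.3 and s = 0.7, the whole-sample risk difference is 4.5 and 10.5 points. The odds ratio is 0.73 and 0.65 with drinkers coded 1, or 0.67 and 0.60 with drinkers coded 0.

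Under ever-use coding the interaction is finite. With equal baselines it is ln(0.692) = −0.368. These are population-averaged figures; equation 1 with its five random effects was not fitted.

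**4. Any use in the recall window, all participants.** The interaction is again estimable, but it concerns current use. The window also changes from lifetime at baseline to 6 weeks or 3 months later, so a student who drank once before college and not since moves from 1 to 0.

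**5. Precision in never-drinkers only.** Half-width of the 95% CI for the risk difference = 1.96 × √[(0.25 + 0.2275)/n], which is 20.2, 15.6 and 13.2 points at n = 45, 75 and 105 at risk per arm (s = 0.3, 0.5, 0.7). At n = 75 the odds ratio interval is exp(−0.619 ± 1.96 × 0.335) = 0.28 to 1.04.

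**The case against.** A reader might infer that the planned model cannot estimate initiation at all. The documents do not support that. Ever-use and recall-window scoring both give finite interactions, and the non-finite case arises only if everyone analysed is 0 at baseline, a coding the Protocol does not choose. Equation 1 is also labelled as the count version, so a logit version is implied; the difficulty is the baseline-referenced contrast, not the log link.

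A reader might also infer that initiation is not measured. It is: the assessment section names the items, and a rule could be built from them. The questionnaires are separate attachments that are not available here, and their wording may define a drink, so the question about a sip may be partly settled there. Criterion 9 concerns willingness, not the outcome.

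Under ever-use coding the useful base rate can be recovered if the baseline row is tabulated: (75 − 50) / (100 − 50) = 50%, ignoring dropout. Coding drinkers 0 hides it.

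Finally, saying that drinkers cannot initiate presumes first-ever use. A definition such as first use since college entry would treat them differently. That is fair, and it is a reason to state the definition. What stands is that the reader is not told which of these readings applies, and that each reading has a consequence for the effect size that the plan names.

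**Conclusion.** The point holds in conditional form and should be fixed. The omission of an event rule, at-risk set and denominator is clear from the text. The misfit of the interactions depends on the coding: no finite estimate if all baseline values are 0, a diluted risk difference if ever-use is scored in all 300, and a different quantity if recall-window use is scored. In the illustration, the control rate ranges threefold (25% to 75%) and the risk difference halves. These sizes rest wholly on the assumed rates and never-drinker share.

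It would be tempting to conclude that the pilot is underpowered for initiation. The documents make no power claim for it, so that conclusion has no basis. The SAP lists only descriptive rates for initiation, so it is affected by the missing event rule and denominator, not by the interaction problem.

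**What to change.** In the Protocol and SAP:
- Analyse initiation among randomised students with no lifetime alcohol use at baseline, and state whether a sip counts as use.
- Score it as cumulative first use since baseline, from the lifetime-use and initiation items already asked at the follow-ups.
- Compare arms at the follow-ups without a baseline outcome row. A follow-up-only logistic mixed model or a discrete-time hazard model keeps the handling of missed waves.
- Report the risk difference and odds ratio with 95% CIs and the at-risk number by arm, and use the same denominator for the SAP's rates.
- Analyse students who drink at baseline for escalation only.
- The SAP is written in the past tense. If outcome data have already been examined, label the at-risk definition post hoc.

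The cost is a few lines of text and a re-tabulation, with no new data. The price is a smaller number and a wider interval for this outcome: about ±15.6 points with 75 at risk per arm under the assumed rates.

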- 3) Describe intended *gender, age range, intended racial and ethnic distribution*. If any vulnerable subjects are involved in this study (e.g., those with limited autonomy or decision-making capabilities), justification must be provided.

We will aim to recruit an equal number of respondents for each age (18, 19) and to sample based on demographics of the University of North Texas.

- 4) Identify the *source(s) from which you will obtain your study population*.

We will reach a wide cross-section of 18-19 year-old first-year college students from the University of North Texas by recruiting via the University of North Texas student directory and in-person recruitment via handouts and flyers at orientation for incoming

first-year students and in residence halls. We will also be posting an ad in the UNT campus magazine, Connections Magazine. Lastly, we will be recruiting online through Virtual Resource Fairs for students who attend an online freshman orientation.

- 5) Describe plans for *recruitment of subjects*. All materials (e.g., flyers, ads, emails, letters, postings, handouts, etc.) to be used for recruiting subjects must be submitted to the IRB for review.

We will utilize a multi-method approach to reach a wide cross-section of college students from the UNT Denton Campus including in-person recruitment (e.g., tabling, distributing flyers and handouts at student dorms), using flyers and advertisements, online recruitment (e.g., submitting a video to Virtual Resource Fairs accessible by freshman students participating in online orientations), and sending student directory email invitations. See General Recruitment above for more information as well as information below.

UNT University Student Directory (see Appendix D)

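### The initiation analysis names only sex and age as covariates and leaves out baseline willingness and intention scores, which gives up a modest amount of precision.

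*Protocol*

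**What the plan says.** Under Data Analysis and Power, the protocol makes initiation a primary outcome: "Primary outcomes are alcohol initiation (binary outcome"). It introduces its mixed model with "The model below represents the basic analytic model for a count outcome". That equation holds time, treatment, their interactions and random effects, but no baseline covariate. The only covariate statement is "We will test sex and age in all analyses".

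Entry is limited to ages 18 and 19 (section F.2), with one allowance: "If a participant screens in at age 19 and turns 20 prior to the start of the pilot study", the participant may stay in. Section F.3 adds "We will aim to recruit an equal number of respondents for each age (18, 19").

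The measures list is headed "Baseline and Follow up Assessments (6-week, 3, 6, 9-month) measures". It includes "The willingness measure will assess willingness to use alcohol in certain scenarios" (alpha .85) and items on intended drinking frequency and quantity (alpha .83). Measures confined to certain waves are marked as such, and these two are not, so both belong to the baseline survey. Neither appears in the analysis section as a covariate or an outcome. Willingness also appears among the inclusion criteria: "Express any level of willingness to take a sip of alcohol".

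The SAP's Analytic Plan reports initiation as yes/no rates at each time point, with no model and no covariates.

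**The concern.** For drinks and consequences, the baseline value is part of the repeated-measures outcome, so a person's starting level informs the model. Initiation differs. Among people who have never drunk, the baseline value is the same for everyone and carries no information. Any precision beyond the raw comparison must come from other baseline variables, and the plan offers only sex and a variable with a very narrow range.

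The initiation effect also rests on a subset of the 300 participants, since only those who have not yet drunk can start. It is therefore the primary outcome where precision is scarcest. Two scores that bear directly on intended or likely drinking are on file at baseline and unused.

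The word *test* adds an ambiguity. It could mean adjusting for sex and age, or examining whether they modify the effect. In a logistic model, adding a prognostic covariate also changes the odds ratio being estimated, from marginal to conditional. The pilot's effect sizes are meant to feed the planning of a later trial, so the reader needs to know which quantity is reported.

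**Working it through.** **Figures in the plan.** 150 + 150 = 300 participants and 300 × 5 assessments = 1500 observations, which matches the protocol. It states no power, alpha, base rate or number of abstainers, so there is no precision target to reproduce.

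**What age can explain.** In whole years with a 50:50 split, Var(age) = 0.5 × 0.5 = 0.25. On the logistic latent scale, the share explained is b²·Var(x) / (b²·Var(x) + π²/3), with π²/3 = 3.29.

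- Assumed odds ratio (OR) 1.35 per year (b = 0.3): 0.0225 / (0.0225 + 3.29) = 0.7%. Assumed ORs of 1.11 and 1.65 give 0.08% and 1.9%.
- Screening collects birth date, so age could be continuous. If uniform over two years, Var = 2²/12 = 0.333, and b = 0.3 gives 0.030 / (0.030 + 3.29) = 0.9%. This is still small.
- A score with Var = 1 and OR 2 per SD: 0.480 / (0.480 + 3.29) = 12.7%. ORs of 1.5 and 3 give 4.8% and 26.8%.

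**Gain from adjusting for both scores.** All inputs are assumptions: 75 abstainers per arm with 20% or 40% initiation, and 40 per arm with 20%. The simulation had a single follow-up, no treatment effect and two standardised scores correlated 0.6, of which one drives initiation. The adjusted estimate comes from a logistic model with treatment and both scores, averaging predicted probabilities over the sample under each arm. The result is the variance of the adjusted risk difference divided by that of the raw one:

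| OR per SD | Variance ratio | Change in variance |
|---|---|---|
| 1 (no prediction) | 1.01–1.03 | 1–3% loss |
| 1.5 | 0.98–1.00 | 0–2% gain |
| 2 | 0.92–0.95 | 5–8% gain |
| 3 | 0.83–0.89 | 11–17% gain |

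Repeat runs moved the ends of these ranges by about 0.01.

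**In interval terms.** With 75 per arm and 40% in both arms, SE = √(2 × 0.4 × 0.6 / 75) = 0.080, so the 95% half-width is 1.96 × 0.080 = 15.7 points. An 8% cut in variance gives 15.7 × √0.92 = 15.0 points. A 17% cut gives 15.7 × √0.83 = 14.3 points.

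**In power terms.** This used one score added to age and sex, an assumed treatment OR of 0.5, an age OR of 1.35 and two-sided 0.05, with 2,500 runs per setting. At 75 per arm and 40% control initiation, power goes from 0.470 to 0.473 (OR 1.5), 0.441 to 0.476 (OR 2) and 0.360 to 0.428 (OR 3). Over all settings tried (50 to 100 per arm, 20% or 40% initiation), the gain was about 0 to 8 points. Age and sex alone changed power by no more than about 1.5 points against treatment only.

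**Validity.** With no treatment effect (75 per arm, 30% initiation, OR 2), the type I error was 0.045 for treatment only, 0.048 with age and sex, and 0.051 with the score added. Leaving the score out does not inflate it.

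**The case against.** The strongest reply is that this is a preference. Leaving a prognostic covariate out of a randomised comparison is legitimate, the study is a pilot with no precision target, and the documents give no figure for how well willingness or intentions predict initiation. All of that stands, and it keeps the point small.

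Other parts of the reply also stand. Participants may skip items and still submit a survey (section G.4), so adjustment needs a rule for missing baseline scores. The entry criterion on willingness removes people with none, which narrows that score's range and may push the gain towards the low end. The protocol does not define the risk set for initiation; restricting it to baseline abstainers is an inference from what initiation means. The SAP is written in the past tense, so a covariate set may no longer be able to count as prespecified.

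A reader might infer more than the documents support:

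- *That the comparison is biased or invalid.* Randomisation protects it, and the type I error above is near 0.05.
- *That covariates will be kept or dropped by significance, outcome by outcome.* The protocol says sex and age in all analyses and describes no selection rule. The wording is only ambiguous.
- *That age has just two values and should go.* Birth date is collected, some participants may have turned 20, and recruitment is stratified on age and sex. Age is weak, but there is no reason to remove it.
- *That the protocol calls willingness a risk marker.* It uses willingness for entry and says nothing about its prognostic strength.
- *That adjustment is free.* It costs 1–3% in variance if the scores are uninformative.

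**Conclusion.** The point holds as a minor improvement. The initiation analysis gains nothing from the baseline outcome among abstainers, names two covariates of which one is nearly constant, and passes over two relevant scores already collected. What is lost is some precision and some protection against chance imbalance. The likely gain lies between nothing and the 5–8% cut in variance at OR 2; the 11–17% figure needs a strong predictor. The size rests on assumed numbers of abstainers, initiation rates and predictor strengths, and on a single-time-point simplification of the mixed model.

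**What to change.** In the protocol's initiation model, state that sex and age are fixed adjusters, and add the baseline willingness and intention scores. If abstainers or events are few, use one score named in advance. Specify no selection by significance, and a simple rule for skipped baseline items, such as imputing the overall mean. If moderation by sex or age is also wanted, say so separately.

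Report a standardised risk difference and risk ratio with 95% CIs beside the SAP's unadjusted rates. This gives a marginal effect that can be carried into planning the later trial. If the mixed model is kept, average the predicted probabilities over its random effects as well. The SAP has no initiation model to amend, so it would need a short paragraph. If the analysis has already been run, label the result supplementary.

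The cost is one or two extra model terms, a few sentences and no new data, with a possible 1–3% loss of precision if the scores predict nothing.
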